8.2 Quantitative Statistical analysis

The characteristics of patients in the different service model types will be summarised using relevant descriptive statistics (proportions, medians, ranges, means, standard deviations, 95% confidence

intervals etc.) before being compared on the basis of each patient socio-demographic, clinical and carer feature using the appropriate bivariate test (including one way ANOVA, chi square and Kruskal Wallis tests, depending on the nature of the variable). Exploratory regression modelling (including logistic regression) will be used in order to investigate the effect of each service model type on the primary outcome (QODD), after controlling for sociodemographic, clinical and carer features. Stepwise regression methods (backward elimination approach, commencing with a set of covariates which have been agreed upon as important by the research team) will be used. The fitted parameters in the final models will indicate if service type is associated with differences in QODD scores. The characteristics of service model types that result in better QODD outcomes will be identified from descriptive data collected at each site as part of the realist evaluation.

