3. STUDY DESIGN

Our research design is informed by realist evaluation [16-17] that will be used to identify candidate programme theories that will be tested and refined throughout the proposed research in order to address our objectives. The funded programme of research will be conducted in 3 phases. This protocol outlines the research and processes for Phase 2 and subsequent Phase 3 consensus events (section 8.5).

Phase 1: Survey

A national telephone survey will be conducted of all known H@H services in the Hospice UK service directory to map the range and variation of H@H services in order to develop a typology of models. This phase has received HRA approval (HRA ref # 17/HRA/0299).

Phase 2: Case studies.

To ensure maximum range, we will purposively select up to 8 case studies of H@H services that vary in model 'type' and location (1-2 case studies per model). 66 patients per model type will be recruited and tracked over time (until death) through data collection from the service provider and the patient's

carer. The primary outcome will be the quality of death and will be collected post death. This will be collected using the Quality of Dying and Death (QODD) tool, a validated interview instrument conducted with bereaved carers [18-20]. Secondary outcomes will include holistic patient assessment (iPOS) [21] and assessment of care by bereaved relatives (VOICES) [22] and service use (AHCR) [23]. Regression analysis will be used to isolate the impact of each service model on quantitative outcomes. An embedded economic analysis will capture resource use and calculate costs. Barriers and enablers to service provision will be explored through in depth interviews with carers, commissioners and providers. Analysis will be iterative with the aim of testing and refining programme theories and to develop provisional context-mechanism-outcome (CMO) configurations. Normalisation Process Theory (NPT) [24] will be used to understand why a model has or has not been embedded within a whole system of care.

[figure not shown]
Phase 3: National consensus workshops.

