8. STATISTICS AND DATA ANALYSIS

8.1 Sample Size

The scores for the primary outcome measure, the QODD, range from 0 to 100. Hales et al 2014 [26] identify 30 and 70 as cut-offs for distinguishing terrible/poor, intermediate and good/almost perfect quality of death. Hence, on the basis of a difference of 10 points representing a meaningful change, and using a standard deviation of 16.41 [27], at least 44 participants in each model type would be required for comparisons between any pair. In order to allow for participant drop out of 33% we propose a sample size of 66 patients per model type (up to 4 models). Our drop out rate is based on a prospective trial of an intervention which followed up with the carers of patients involved who were sent the 24 item QODD questionnaire by post 4-6 months post death. They received a 55.4% response rate and we predict that the contact through bereavement services and phone interview approach we propose will achieve a better response than the postal survey approach used in this study [28].

Based on estimated H@H service size and annual throughput of patients we estimate that recruitment of 66 per model type is achievable for medium and large units in particular. The National Minimum Data Set 2013/14 by the National Council for Palliative Care [29] grouped H@H services by size into roughly 3 equal groups:

- Small fewer than 191 patients per annum
- Medium 191-310 patients per annum
- Large more than 310 patients per annum

However our final range of models and possible case study sites is unknown until interpretation of the phase 1 survey results. If sites are smaller it will be possible to recruit two or more case study sites of the same model type to reach the overall sample size of 66. In the final regression modelling process (outlined below) we would be able to employ a dummy variable to distinguish between the two providers to check for differences.

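### Backward elimination is the only adjusted analysis of QODD in a non-randomised comparison; it can drop agreed confounders and understate the uncertainty of the service-model contrasts

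*Protocol*

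**What the plan says.** Section 8.2 of the protocol describes one route to an adjusted comparison of the primary outcome. It opens with "Exploratory regression modelling (including logistic regression) will be used in order to investigate the effect of each service model type" on QODD, "after controlling for sociodemographic, clinical and carer features". The covariates are chosen by "Stepwise regression methods (backward elimination approach, commencing with a set of covariates which have been agreed upon as important by the research team". The conclusion is read from what remains: "The fitted parameters in the final models will indicate if service type is associated with differences in QODD scores". The section gives no elimination threshold, names no covariate that must stay, and provides no full-model result to set beside the reduced one.

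Two statements in section 3 set the context. Sites are not randomised: "we will purposively select up to 8 case studies of H@H services". The purpose given for the regression is stronger than exploration: "Regression analysis will be used to isolate the impact of each service model on quantitative outcomes". Section 8.1 sizes the study on a mean difference, "on the basis of a difference of 10 points representing a meaningful change", with a standard deviation of 16.41, 44 evaluable patients per model type, and 66 recruited per type for up to four types.

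**The concern.** In a comparison of purposively chosen services, differences in case mix between models are the main threat, and regression adjustment is the only quantitative protection described for QODD. A covariate matters as a confounder when it both predicts QODD and differs between models. Backward elimination tests only the first condition, and at this sample size it tests it with little power for modest predictors. A covariate the team has agreed is important can therefore be deleted because its coefficient is not significant, even if it is unevenly spread across models. Its effect then passes into the service-model contrast.

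The final model is also read as though it had been specified in advance. Its standard errors take no account of the selection, so they can be too small and the confidence intervals too narrow. Section 11 promises guidelines on which models work best, so these contrasts will be used as effect estimates.

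**Working it through.** **1. The plan's own figures.** Section 8.1 states neither alpha nor power; two-sided 5% and 80% are assumed.
- n per group = 2 × (1.960 + 0.842)² × 16.41² / 10² = 42.3, so 43 by the normal approximation. With the noncentral t, power is 79.8% at 43 and 80.7% at 44, so 44 is reproduced.
- 44 / (1 − 0.33) = 65.7, so 66 is reproduced.
- Evaluable total: 4 × 44 = 176. Unadjusted standard error of a pairwise contrast: 16.41 × √(2/44) = 3.50 points.

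**2. Chance of keeping a weak confounder.** Take a covariate worth 0.1 SD of QODD per SD. Its test statistic is centred near 0.1 × √176 = 1.33. The chance of passing p<0.05 is about P(Z > 1.96 − 1.33) = 26%. The simulations agree: 1.3-1.4 of 5 such confounders were kept in one set of runs and 2.7-2.8 of 10 in another.

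**3. Bias from dropping it.** For uncorrelated covariates this is about strength × imbalance × 16.41. One covariate of 0.1 SD with a 0.3 SD imbalance leaves 0.1 × 0.3 × 16.41 = 0.5 points. With ten such covariates, all in the same direction, no adjustment at all leaves 10 × 0.5 = 4.9 points before rounding.

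**4. Simulations.** All use four types of 44, SD 16.41, no true service effect and service-type terms always kept, with 1,200 or 1,500 runs. Monte Carlo error at a 5% rate is therefore about 0.6 percentage points. Confounder strengths, imbalances and thresholds are assumptions.

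Ten covariates of 0.1 SD, with one model's case mix shifted (ranges are across repeat simulations):

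| Scenario | Threshold | Bias after elimination (points) | Type I error after elimination |
|---|---|---|---|
| No imbalance | p>0.05 | about 0 | about 5% |
| Mixed (random) directions, shift 0.2-0.5 SD | p>0.05 | about 0 on average | 6-11% |
| 3 of 10 shifted by 0.3 SD, same direction | p>0.05 | 0.8 | 7-8% |
| All shifted by 0.2 SD, same direction | p>0.05 | 1.4-1.6 | 9-10% |
| All shifted by 0.3 SD, same direction | p>0.05 | 2.4-2.5 | 14% |
| All shifted by 0.5 SD, same direction | p>0.05 | 3.8-4.1 | 23-27% |
| All shifted by 0.3 SD, same direction | p>0.20 | 1.0 | 7-8% |

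In the same-direction scenarios with all ten shifted, keeping all ten covariates gave bias of about 0 and type I error of 4-6%.

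A second set used five true confounders of 0.10-0.20 SD, all acting in one direction and graded 0.3-0.5 SD between the extreme types, plus five noise covariates. The threshold was 0.05 or 0.10.
- Elimination: bias 0.3-2.0 points, type I error 5.5-12.5%, 95% interval coverage 87.5-94.5%.
- Full model: bias −0.2 to +0.1 points, type I error 3.9-6.0%, coverage 94.0-96.1%.
- With no imbalance, elimination gave no bias and 5.3% type I error.

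**5. Standard errors.** In the worst of these five-confounder runs (0.10 SD, 0.5 SD imbalance, p>0.05), elimination reported a mean standard error of 3.50 against an actual spread of 3.96, a ratio of 3.96 / 3.50 = 1.13. The full model reported 3.79 against 3.86, a ratio of 1.02. The reported standard error rises by 3.79 / 3.50 − 1 = 8%, yet the full model's estimates are, if anything, less variable (3.86 against 3.96). Across all scenarios the rise in reported standard error was about 2% (3.24 to 3.31) to 12%.

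**The case against.** **Exploratory label and agreed starting set.** Section 8.2 calls the modelling exploratory and starts from covariates chosen on substantive grounds. Both soften the point. Neither removes it: section 3 says the regression will isolate each model's impact, and elimination can discard the very covariates that were agreed.

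**The size is assumed.** This stands. The protocol gives no imbalance, no confounder strengths and no threshold, and a threshold may be set in an analysis plan not shown here. The largest figures need every covariate to be imbalanced in one model and to push QODD the same way. A lenient threshold removes more than half of the bias in the 0.3 SD case (2.4 to 1.0 points).

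**Elimination beats no adjustment.** In the same-direction scenarios this is so: unadjusted bias was 3.3, 4.9 and 8.2 points at shifts of 0.2, 0.3 and 0.5 SD, and elimination removed about half. But the relevant alternative is the full agreed set, which removed essentially all of it.

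**Two stronger readings that the documents do not support.** A reader might infer that service model type could itself be eliminated, leaving no estimate. Section 8.2 applies elimination to the covariates and says the final models will report on service type, so its natural reading keeps that term in. A reader might also infer that logistic regression means the primary analysis dichotomises QODD and loses power. The section only lists it among the methods and describes the result as differences in scores; nothing makes a cut score the primary analysis.

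**Conclusion.** The concern holds as a fault in a stated method, not as a missing detail. Elimination by outcome significance is the wrong criterion for controlling confounding, and here it is the only adjusted analysis of the primary outcome. It can drop agreed confounders, can bias the service-model contrasts, and where case mix differs between models it gives standard errors that are too small.

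The harm ranges from negligible (no imbalance, type I error about 5%) through modest (6-11%, no average bias, mixed directions) to serious (9-27% and about 1.5-4 points against the 10-point target). The serious end belongs to the aligned worst case at an assumed p>0.05. Where between these the study would fall cannot be judged from the protocol. The change should be made because the alternative performed better in the scenarios with imbalance and costs very little.

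**What to change.** In section 8.2, make the main adjusted result one linear regression of the QODD score that contains service model type and every covariate in the team's agreed set, with no data-driven deletion. Fix that set before the outcome data are examined. Report backward elimination, and any logistic model, only as sensitivity analyses.

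The cost is a few sentences and no new data. With four types and ten single-term covariates the model has 1 + 3 + 10 = 14 parameters on about 176 observations. The reported standard error was about 2-12% larger in the scenarios above, part of which corrects an understatement. The cost would be somewhat higher if covariates with many categories, or the provider indicator mentioned in section 8.1, were added.

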8.3 Qualitative data analysis

Interviews will be transcribed and uploaded into NVivo 10 to assist with data management and analysis. Analysis will be iterative with the aim of testing and refining programme theories and further developing provisional context-mechanism-outcome (CMO) configurations [17]. As described above, Normalization Process Theory (NPT) will be used to understand why a model has or has not been embedded within a whole system of care [24], and Burden of Treatment (BOT) will be used to understand the impact of the model on patients and carers. NPT offers a well-established framework for analysis in order to understand implementation processes through the perspectives of multiple stakeholders including: service users; service providers and commissioners [30]. Constructs from the NPT framework will form the basis of a deductive coding structure. Analysis will also seek to identify any emergent themes not covered by NPT. Synthesis of an NPT informed coding framework alongside an inductive approach [31] allows for a focused and yet open qualitative approach that allows unexpected findings to emerge [30]. As a theory-led investigation that uses a deductive and inductive approach to coding, we will use a stopping criterion of 3 interviews with no new themes coded in order to achieve data saturation [25].

8.4 Economic analysis

The economic analysis will be at two levels. First, a descriptive analysis will be conducted of the resources and costs of running each case study H@H service. This will cover: staff; service facilities, equipment, overheads; transport for home care; other sundry items associated with care delivery. These data will be collected at interview with service managers. Where hospices provide community or inpatient services in addition to the H@H, guidance on appropriate attribution of costs will be sought from the finance manager. Information on activity rates will also be gathered so that costs per patient receiving H@H can be calculated and compared between case studies. Second, a patient level analysis will be undertaken. Due to the nature of this study, patients recruited will likely have short and variable life expectancy, leading to an inconsistent time horizon for the individual patient level data captured. This lack of a normalised time integrated measure of health outcome (such as a QALY) or cost, will make a traditional comparative cost -effectiveness analysis problematic. Hence, the economic analysis will be limited to a descriptive analysis of service utilisation and cost for the different H@H models. Whole system resource use in the end-of-life care will be captured prospectively from the point of recruitment to the study for each patient. At first interview, participants will be asked to report retrospectively, via recall, on service use for the two months prior to recruitment. Service utilisation data will cover primary, community, hospital, hospice, social care, voluntary and informal care received. A customised version of the Ambulatory and Home Care Record (AHCR) [23] will be used for this purpose.

Service use data, once captured, will be grouped into 4-6 time periods of approximately equal sample size, delimited by survival time following start of service use data collection. The cut points

will be determined by the distribution of the data. In our previous study [9], 6% of patients referred to a H@H service had died within 2 days, 40% within one month, 62% within 2 months, and the remaining 38% were refer red over 2 months before death. Resource use will be converted to costs using national tariffs [32]. Informal care will be valued using replacement cost methods. For each of the model types of H@H service provision, an average cost/day of treatment will be estimated for the 4-6 time periods respectively. This will provide descriptive cost data, independent of expected survival time that can be compared between H@H model types. Alongside this analysis, a comparison of the average survival times for patients in each of the H@H models will be provided. However, caution will need to be taken when trying to infer a total cost of service from the survival data and average cost of service/day. Costs will be presented as means and median, given the typical skew in the distribution of costs. Comparison of costs between H@H model will be assessed for significance using Mann Whitney test. Sensitivity analysis for costs will be handled deterministically, varying the amount of resource use between their upper and lower limits for each H@H model type. Costs will be analysed in relation to outcomes from different models in a cost –consequences framework.

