- Other relevant services operating in area, e.g. Marie Curie arrangements, 24h district nursing, other charities (e.g. Cross Roads, Age Concern), Continuing Healthcare funding and services. How do they integrate/liaise with other service providers?
- Access to palliative care beds: hospice beds, palliative care beds in other settings.
- Activity data for previous year: number of referrals, demographic characteristics of patients referred (age, sex, cancer/non cancer), duration in service, number of patients without a family carer in the home, total number of service hours received per patient, number of referrals rejected.
- Staffing e.g. HCAs, registered nurses, doctors and Allied Health Professionals and time allocated to HAH.
- Facilities and equipment, availability and access.
- Medications, availability and access, who gives injectable medications in an emergency?
- Referral criteria e.g. actively dying in hours/days, prevention of hospital admission, longer term care.
- How the service operates: how are referrals made? will referrals be actioned 24/7?, response time from 1st referral, assessment process (before service is accessed), out of hours visiting (which staff?), lengths of interventions (e.g. 1h, 2h, 4h, full shifts in the home), frequency of interventions available, how do patients exit the service (e.g. numbers experiencing transfer of care to social care packages, hospice or hospital admission, death).
- Service budget: income sources (NHS, Local Authority social care, donations, other) and expenditure categories (patient facing staff, administrative support, facilities, equipment, overheads).
- Outcomes: what data are collected? How are they performing against the agreed outcomes measured (e.g. death at home, responding within 4 hours to crisis), preferred place of death, actual place of death.
- Barriers and enablers to providing the defined service. If it has changed from its original brief, what is this and why.

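### The service-level cost comparison rests on cost per patient alone, which moves with length of stay; cost per patient-day and per care hour should stand beside it

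*Protocol*

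**What the plan says.** Section 8.4 of the phase 2 protocol sets out two levels of economic analysis.

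- **Service level.** "First, a descriptive analysis will be conducted of the resources and costs of running each case study H@H service". Staff, facilities, equipment, overheads and transport are covered, from interviews with managers. Activity rates are then to be gathered so that "costs per patient receiving H@H can be calculated and compared between case studies". The term for activity is not defined there, and no day, hour or length-of-stay denominator is named.
- **Patient level.** The protocol recognises that "patients recruited will likely have short and variable life expectancy, leading to an inconsistent time horizon for the individual patient level data captured". It concludes that a conventional cost-effectiveness comparison would be problematic and limits itself to description. Resource use is priced at national tariffs and, for each model type, "an average cost/day of treatment will be estimated for the 4-6 time periods respectively". The protocol presents this as free of dependence on survival, and average survival by model is to be shown alongside.

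The phase 1 protocol (section 6, Research Plan / Methods) bears on whether stays differ. Its examples of referral criteria are "actively dying in hours/days, prevention of hospital admission, longer term care". Its activity items include duration in service and "total number of service hours received per patient". Its data analysis text cites an earlier survey in which two groupings of providers differed in, among other things, reasons for referral and how long episodes lasted.

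**The concern.** Cost per patient combines what a day of the service costs with how many days a patient receives it. If one service takes people mainly in their last days and another supports them for weeks, the second has the higher cost per patient even when a day of care costs the same in both.

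The protocol sees this problem at patient level and answers it with cost per day. It does not carry the answer to the service level, which is the only place where each service's own running costs are described. With one or two case studies per model type (section 3, Study Design), a comparison between case studies has little averaging within a model and can easily be read as a comparison of models.

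Objective 2 (section 2) concerns the resource implications and costs of care in each model, and the guidance promised in section 11 is to cover cost as well as effectiveness. A commissioner shown cost per patient alone could take a difference in admission timing for a difference in the cost of care.

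**Working it through.** The plan gives no cost figure, so there is none to reproduce. The check has three steps.

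**1. How the measure behaves.** For service *s*, with daily cost *c* and mean days in service *L*:

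cost per patient(s) = c(s) × L(s)

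For services A and B, the ratio of cost per patient is [c(A)/c(B)] × [L(A)/L(B)]. With equal daily cost this is L(A)/L(B), whereas the ratio of cost per patient-day is 1.0 whatever the stays.

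**2. Illustration, all inputs assumed.** Daily cost £100 in both services; mean stays 14 and 60 days.

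- Cost per patient: 14 × £100 = £1,400 and 60 × £100 = £6,000.
- Ratio: 60/14 = 4.3, with no difference in daily cost.
- In reverse, for cost per patient to be equal, the short-stay service's daily cost would have to be 4.3 times the other's: £6,000/14 = about £429 against £100.

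**3. Can the documents supply the size?** The only distribution given is time from referral to death in the earlier study cited in section 8.4: 6% within 2 days, 40% within one month, 62% within two months, 38% later. The bands are therefore 6%, 34%, 22% and 38%. Assume midpoints of 1, 16 and 45 days, and 60 to 120 days for the open band.

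- Mean for deaths within a month: (0.06 × 1 + 0.34 × 16)/0.40 = 13.75 days.
- Mean for later deaths: (0.22 × 45 + 0.38 × 60)/0.60 = 54.5 days, up to (0.22 × 45 + 0.38 × 120)/0.60 = 92.5 days.
- A service with an 80/20 short/long mix has a mean of 0.8 × 13.75 + 0.2 × 54.5 = 21.9 days (29.5 with the longer tail).
- A service with a 20/80 mix has a mean of 0.2 × 13.75 + 0.8 × 54.5 = 46.4 days (76.8 with the longer tail).
- Ratio of cost per patient at equal daily cost: 2.1 to 2.6.

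This range depends on the assumed mixes and midpoints. The protocol gives no mean stay by service or model, and time from referral to death only stands in for time in service, since the phase 1 survey also asks about exits to social care packages, hospice and hospital. The direction follows from the arithmetic; the size does not follow from the documents.

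**The case against.** The strongest reply has four parts.

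- **The denominator may be intended.** Activity rates are undefined in section 8.4, and the phase 1 list of activity data includes duration and hours. The detail could sit in an analysis plan that is not shown. This stands in part: the data may well be collected. But the protocol does name the measure to be compared, and it is cost per patient only.
- **Models are compared elsewhere with time adjustment.** Cost per day within survival periods, with average survival beside it and a cost-consequences framework, is planned by model type. This is a real mitigation. It covers resource use at national tariffs, however, and leaves each service's own running costs unadjusted.
- **Cost per patient is a legitimate figure.** A service that supports people for longer does use more resource per patient, and a budget holder needs to know that. Moreover, if care is more intensive near death, cost per day alone would make late-admitting services look dear. This stands, and it argues against replacing one measure with the other.
- **Differing stays are not shown.** The referral criteria are survey examples, the earlier survey's differences are cited without size, and the typology figure is not shown. This stands, so the point is conditional.

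Two stronger readings are tempting. A reader might infer that services would be ranked by length of stay. The documents plan no ranking, and this level is descriptive with no test named. A reader might also scale the referral-to-death distribution up and down and treat the resulting gap as the plan's own. Scaling by 0.8 and 1.25 returns 1.25/0.8 = 1.6, and by 0.5 and 1.5 returns 3.0, whatever the distribution, so those gaps are only the chosen factors.

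**Conclusion.** The point holds in a limited form. At service level the only comparison named is cost per patient, and if mean stay differs between case studies, that measure differs in proportion at equal daily cost. The patient-level cost per day does not correct this for services' own running costs.

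The size is unknown. The 4.3-fold figure rests on assumed stays of 14 and 60 days and equal daily cost; the 2.1- to 2.6-fold range rests on assumed mixes and band midpoints. Unequal daily intensity could narrow or reverse the gap. Because the analysis is descriptive and untested, and time-adjusted costs by model are planned separately, this is a cheap improvement and not a fault that undermines the economic analysis.

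**What to change.** In section 8.4, at the service level:

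- keep cost per patient, and report beside it cost per patient-day in service and cost per hour of care delivered;
- show mean duration in service and mean hours per patient for the same financial year as the cost data;
- state that differences in cost per patient between case studies will not be interpreted without these.

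This takes a sentence or two and two extra denominators. The phase 1 survey already asks services for duration and hours, but the case study sites would need to supply them for the year of the cost data. Services with poor hours records will need an estimate, which should be labelled as such. No single measure is neutral if intensity rises near death, so they should be shown together.

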4. STUDY SITES

The findings from phase 1 were used to create a H@H service model typology comprising 4 model types (see Figure 1). This forms a sampling framework to select case study sites from H@H services in England (ideally from hospices responding to the phase 1 survey). Each type of H@H service within the typology will be represented by one or more case study sites. We also anticipate that the sample will incorporate geographical spread, mixture of deprivation populations and include services that are innovative or more traditionally delivered. Case study sites will be invited by the Chief Investigator to participate.

Figure 1: H@A service model typology

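### Costs of four service model types are to be tested with a two-group rank test that does not address the mean cost per day the section estimates

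*Protocol*

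**What the plan says.** All of this is in the protocol; no SAP is shown.

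- **Number of groups.** Section 4: "The findings from phase 1 were used to create a H@H service model typology comprising 4 model types".
- **Declared scope.** Section 8.4 first says that "the economic analysis will be limited to a descriptive analysis of service utilisation and cost for the different H@H models".
- **Survival periods.** Service use is to be "grouped into 4-6 time periods of approximately equal sample size, delimited by survival time following start of service use data collection".
- **Quantity estimated.** For each model type, "an average cost/day of treatment will be estimated for the 4-6 time periods respectively". The section adds: "This will provide descriptive cost data, independent of expected survival time that can be compared between H@H model types".
- **Summaries.** "Costs will be presented as means and median, given the typical skew in the distribution of costs".
- **Test.** "Comparison of costs between H@H model will be assessed for significance using Mann Whitney test".

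Section 8.4 names no four-group test for costs and no rule for multiple comparisons. It does not say whether the test is run within the survival periods or on costs pooled over them, or which pairs are compared. Section 8.2, on patient and carer characteristics across the same model types, does name multi-group tests, including one-way ANOVA and Kruskal-Wallis.

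**The concern.** There are three separate difficulties.

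1. **The test does not fit the number of groups.** Mann-Whitney compares two samples. With four model types it yields a set of pairwise p-values and no single answer on whether costs differ by model. Without an overall test or an adjustment, chance differences may be reported as significant.
2. **The test does not address the quantity estimated.** The section estimates an average cost per day. Mann-Whitney asks whether values in one group tend to rank above those in the other. When costs are skewed and spreads differ between models, means and ranks can point different ways.
3. **A significance test sits awkwardly beside the declared descriptive scope.**

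The resource implications and costs of each model are the second study objective (Section 2). Section 11 promises guidelines telling services and commissioners which models work best and at what cost. Commissioners budget on mean cost, so a rank-based p-value could mislead in the output the study is meant to deliver.

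**Working it through.** **Inputs.** Four model types (Section 4); 4-6 survival periods (Section 8.4); 44 evaluable and 66 recruited patients per model type (Section 8.1). A two-sided 0.05 per test is my assumption, since the protocol states no significance level.

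**The plan's own figures.** The protocol states no number of cost tests, so there is none to reproduce. The group sizes used below come from the QODD calculation, which does reproduce. With a difference of 10, SD 16.41, two-sided 0.05 and 80% power (both assumed), 2 × (1.96 + 0.84)² × 16.41² / 10² gives 43 per group. The t-test version gives 43.25, rounded up to 44. Then 44 / (1 − 0.33) = 65.7, rounded up to 66.

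**Number of tests.** Pairs among four types: 4 × 3 / 2 = 6. If run in every period: 6 × 4 = 24, 6 × 5 = 30 or 6 × 6 = 36. Average patients per model per period run from 44 / 6, about 7, to 66 / 4, about 16.

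**False positives with no true difference.** The independence figure is 1 − 0.95^k. It is too high here because pairs share groups, so pairwise Mann-Whitney tests on four identical distributions were also simulated.

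| Use of the test | Tests | Expected false positives | Independence | Simulated |
|---|---|---|---|---|
| All pairs, unbanded | 6 | 6 × 0.05 = 0.3 | 26.5% | 16-20% |
| All pairs, 4 periods | 24 | 24 × 0.05 = 1.2 | 70.8% | 57-60% |
| All pairs, 6 periods | 36 | 36 × 0.05 = 1.8 | 84.2% | 66-73% |

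For the unbanded case, short simulation runs gave 16-19% and a run of 40,000 replicates at 44 per group gave 20.2%. The large-sample value, from the studentised range for four groups at 1.96 × √2 = 2.77, is 20.3%, so about 20% is the best single figure. It also fits the banded rows: 1 − (1 − 0.203)^4 = 60% and 1 − (1 − 0.203)^6 = 74%. The simulated banded figures are slightly lower because the test is conservative in small cells.

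For comparison, one overall four-group test has a 5% error rate. One such test in each period means 4-6 tests and 1 − 0.95^4 = 18.5% to 1 − 0.95^6 = 26.5%.

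**Ranks against means.** The protocol gives no cost spread, so log-normal costs with assumed log-SDs were simulated at 11 to 66 per group. For equal means the ratio of medians is exp((s₂² − s₁²) / 2).

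- Log-SD 0.8 vs 1.0, equal means: medians differ by exp((1.00 − 0.64) / 2) = 1.2-fold; rejected in about 7-20% of tests.
- Log-SD 0.5 vs 1.2, equal means: medians differ by exp((1.44 − 0.25) / 2) = 1.8-fold; rejected in about 29-93%.
- Log-SD 0.5 vs 1.2, equal medians and means 1.8-fold apart: rejected in only about 5-7%.

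The test can therefore reject when mean costs are equal, and have almost no power when means differ substantially. How often depends on how unlike the spreads are.

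**The case against.** **The bands and the six pairs are not in the test sentence.** This stands. The sentence naming the test mentions neither. A reader might infer that 24-36 tests are planned, because banded cost per day is the patient-level quantity offered for comparison. That is a natural reading, but the text does not state it, so 24-36 is an upper range. If all pairs are compared once without bands, the count is six.

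**Which pairs, which strata and what adjustment commonly belong in an SAP.** This stands for the details. It does not rescue the test itself: the protocol names a specific two-group method for a four-group comparison.

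**The rank-against-mean example rests on assumed spreads.** This stands in part. In the wider pair, medians really do differ 1.8-fold, so the rejections reflect a genuine difference in typical cost. The milder pair shows a much smaller effect. The protocol also reports means and medians together, so a reader would see both, and it nowhere says that Mann-Whitney tests means. What remains is that the only p-value offered does not refer to the average the section estimates.

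**The descriptive statement chiefly rules out a cost-effectiveness analysis.** This largely stands. A reader might infer an outright contradiction, but the statement follows from the argument that no time-normalised outcome or cost is available, and the section then says the costs can be compared between models. It is a tension in wording.

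**Costs are not the primary outcome.** True: QODD is primary, and no decision rule depends on a cost p-value. This limits the seriousness.

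**Conclusion.** The point holds as a wrongly chosen method stated in the protocol. A two-group rank test is fixed for four groups, in a section whose estimate is an average cost per day. Followed as written, it can only produce pairwise p-values that do not test that average.

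The multiplicity cost is about 16-20% for at least one chance finding over six unbanded pairs. It is about 57-73% only if every pair is tested in every period. Both assume 0.05 per test, no adjustment and no true difference, and the second also assumes a use of the test that the protocol does not state. The disagreement between ranks and means is certain in principle, but its size cannot be read from the documents: about 7-20% rejection under one assumed pair of spreads with equal means, about 29-93% under another.

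The documents do not show that models will be wrongly called cheaper or dearer, only that they may be. The sentence should be changed, but the point does not threaten the primary analysis.

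**What to change.** In Section 8.4, replace the Mann-Whitney sentence with the following.

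- Report differences in mean cost per day between model types with bootstrap 95% confidence intervals, alongside the means and medians already planned. Say whether the comparison is pooled over the survival periods or made within them.
- If a significance test is kept, use one overall four-group test. Kruskal-Wallis is already named in Section 8.2 and would solve the number-of-groups problem. It too compares ranks, so it should not be presented as a test of mean cost.
- Label period-by-model figures as descriptive, with no p-values.
- Reword the scope statement so that it agrees with whatever inference remains, for example by saying that it excludes a cost-effectiveness analysis. The alternative is to drop significance testing of costs altogether.

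A regression model for cost is one acceptable route to the mean differences but is not needed to correct the text. The cost is one reworded sentence, a matching edit to the scope statement and a little more analysis code. There are fewer p-values to report, and no change to data collection or sample size.
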